
2.8.1.1 Adverse events of special interest / grouping of AEs

The following (S)AEs of special interest were defined:

- Neutropenia (MedDRA Code 10029354)
- Hepatobiliary toxicity, defined as grade 3 or 4 increases in ALT or/and AST (MedDRA Codes: 10001551, 10003481)
- QT prolongation (MedDRA Code 10014387)

In addition, the time to occurrence from start of study drug to the (first) onset of a TEAE of special interest (TEAESI) is analysed by sample statistics as well as the duration (start – end + 1 day). Further the number of TAEASI occurring in one patients during on-treatment period is displayed.

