Majority of the patients experienced at least one AE in both treatment groups (98.5% vs. 97%); the most commonly ($\geq 30\%$) reported AEs in ribociclib plus letrozole group irrespective of causality were: neutropenia (60.8%), nausea (51.5%), fatigue (36.5%), diarrhea (35%), and alopecia (33.2%). AEs where a higher proportion of ribociclib plus letrozole-treated patients reported events (and where there was a $\geq 10\%$ difference to the placebo plus letrozole group) included neutropenia (+56.6%), nausea (+23%), decreased neutrophil count (+18%), alopecia (+17.7%), decreased white blood cell count (+17.4%), vomiting (+13.8%), anemia (+13.8%), diarrhea (+12.9%), leukopenia (+12.9%), increased ALT (+11.7%), and increased AST (+11.4%). The incidence of SAEs was 21.3% and 11.8% in the ribociclib plus letrozole and placebo plus letrozole arms, respectively. Twenty-five patients (7.5%) from the ribociclib plus letrozole group experienced SAEs that were considered by the Investigator to be related to study treatment. Febrile neutropenia was the only suspected SAE reported in $>1\%$ of patients (1.2%). Permanent discontinuations due to adverse events was reported in 7.5% of patients receiving ribociclib plus letrozole and 2.1% in patients receiving placebo plus letrozole. The most common AEs leading to treatment discontinuation of both ribociclib and letrozole were ALT increased (2.7%), AST increased (2.4%) and vomiting (1.5%).

Neutropenia, QT prolongation and hepatobiliary toxicity are important identified risks with ribociclib treatment:

- Neutropenia, irrespective of causality, was the most common adverse event in the ribociclib plus letrozole arm. All grade neutropenia occurred in 60.8% of patients, with grade 3 neutropenia in 39.5% and grade 4 in 8.7% of patients. There were five (1.5%) cases of febrile neutropenia.
- Grade 3 or 4 increases in ALT (10.2% vs. 1.2%) and AST (6.9% vs. 1.5%) were reported in the ribociclib plus letrozole and placebo plus letrozole arms respectively. Four patients met the criteria for Hy's Law in ribociclib plus letrozole group, 3 of these cases were confirmed with biopsies. All liver function test elevations in these patients were reversible and returned to normal values after stopping ribociclib.

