Table 1-5 Adverse events with suspected relationship to study treatment in study (CLEE011A2301)

Adverse events with suspected relationship to study treatment by preferred term and maximum grade (greater 5% in either arm) (Safety set)	Ribociclib + Letrozole n=334			Placebo + Letrozole n= 330		
Preferred Term	All grades (%)	Grade 3 n (%)	Grade 4 n (%)	All grades n (%)	Grade 3 n (%)	Grade 4 n (%)
Total	319 (95.5)	199 (59.6)	43 (12.9)	249 (75.5)	27 (8.2)	1 (0.3)
Neutropenia	199 (59.6)	130 (38.9)	29 (8.7)	13 (3.9)	2 (0.6)	0
Nausea	144 (43.1)	6 (1.8)	0	54 (16.4)	0	0
Alopecia	95 (28.4)	0	0	44 (13.3)	0	0
Fatigue	92 (27.5)	5 (1.5)	1 (0.3)	64 (19.4)	2 (0.6)	0
Diarrhea	72 (21.6)	3 (0.9)	0	39 (11.8)	0	0
Neutrophil count decreased	63 (18.9)	44 (13.2)	3 (0.9)	3 (0.9)	1 (0.3)	0
Vomiting	62 (18.9)	6 (1.8)	0	22 (6.7)	1 (0.3)	0
White blood cell count decreased	57 (17.1)	37 (1.1)	2 (0.6)	5 (1.5)	1 (0.3)	0
Hot flush	51 (15.3)	1 (0.3)	0	63 (19.1)	0	0
Arthralgia	48 (14.4)	1 (0.3)	0	52 (15.8)	1 (0.3)	0
Leukopenia	48 (14.4)	25 (7.5)	1 (0.3)	9 (2.7)	1 (0.3)	0
Anemia	46 (13.8)	2 (0.6)	0	9 (2.7)	3 (0.9)	0
Rash	45 (13.5)	2 (0.6)	0	10 (3.0)	0	0
Alanine aminotransferase increased	42 (12.6)	22 (6.6)	5 (1.5)	8 (2.4)	1 (0.3)	0
Constipation	40 (12.0)	0	0	20 (6.1)	0	0
Decreased appetite	39 (11.7)	3 (0.9)	0	18 (5.5)	0	0
Aspartate aminotransferase increased	36 (10.8)	12 (3.6)	2 (0.6)	8 (2.4)	3 (0.9)	0
Stomatitis	33 (9.9)	1 (0.3)	0	15 (4.5)	0	0
Pruritus	30 (9.0)	1 (0.3)	0	3 (0.9)	0	0
Asthenia	27 (8.1)	1 (0.3)	0	23 (7.0)	1 (0.3)	0
Headache	27 (8.1)	1 (0.3)	0	24 (7.3)	0	0
Dysgeusia	23 (6.9)	0	0	12 (3.6)	0	0
Dry mouth	21 (6.3)	1 (0.3)	0	14 (4.2)	0	0
Dizziness	19 (5.7)	0	0	21 (6.4)	0	0
Thrombocytopenia	19 (5.7)	1 (0.3)	0	0	0	0
Lymphocyte count decreased	18 (5.4)	12 (3.6)	0	3 (0.9)	2 (0.6)	0

The ongoing phase III study MONALEESA-3 (CLEE011F2301) investigates ribociclib in combination with the selective estrogen receptor degrader fulvestrant for the treatment of men and postmenopausal women with hormone receptor positive, HER2-negative, advanced breast cancer who have received no or only one line of prior endocrine treatment. Premenopausal patients are currently investigated in the ongoing phase III study MONALEESA-7 (CLEE011E2301), which is a randomized, double-blind, placebo-controlled

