8.1.2 Laboratory test abnormalities

8.1.2.1 Definitions and reporting

Laboratory abnormalities that constitute an Adverse event in their own right (are considered clinically significant, induce clinical signs or symptoms, require concomitant therapy or require changes in study treatment), should be recorded on the Adverse Events CRF. Whenever possible, a diagnosis, rather than a symptom should be provided (e.g. anemia instead of low hemoglobin). Laboratory abnormalities that meet the criteria for Adverse Events should be followed until they have returned to normal or an adequate explanation of the abnormality is found. When an abnormal laboratory or test result corresponds to a sign/symptom of an already reported adverse event, it is not necessary to separately record the lab/test result as an additional event.

Laboratory abnormalities, that do not meet the definition of an adverse event, should not be reported as adverse events. A Grade 3 (severe) or 4 (life-threatening) event as per CTCAE does not automatically indicate a SAE unless it meets the definition of serious as defined below and/or as per investigator's discretion. A dose hold or medication for the lab abnormality may be required by the protocol in which case the lab abnormality would still, by definition, be an adverse event and must be reported as such.

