1.2 Study objectives and endpoints

Objectives and related endpoints are described in the table below (in accordance with Table 3-1 from the protocol).

Primary Objective	Endpoint

The primary objective of this study is the assessment of the clinical benefit rate after 24 weeks for the total population and for cohorts A and B separately:
 
1. Cohort A: postmenopausal women and men who received no prior treatment for advanced disease. (70% group)2. Cohort B: pre-, and perimenopausal women who received no prior treatment for advanced disease as well as pre-, peri- and postmenopausal women and men who received no more than 1 prior chemotherapy and 2 prior lines of endocrine therapy for advanced disease (30% group)	Clinical Benefit Rate (CBR) after 24 weeks of treatment as defined by RECIST 1.1 as percentage of patients with CR, PR or SD until week 24 or longer as well as patients with NCRNPD >24 weeks for patients with non-measurable disease

Secondary Objectives	Endpoint

To assess the clinical benefit rate (CBR) after 24 weeks among Cohort B1 and B2:
	
Clinical Benefit Rate (CBR) after 24 weeks of treatment as defined by RECIST 1.1 as percentage of patients with CR, PR or SD until week 24 or longer as well as patients with NCRNPD >24 weeks for patients with non-measurable disease

Progression-free survival (PFS) for the three different populations: Cohort A, Cohort B1, Cohort B2
	
PFS based on radiologic assessment by investigator using RECIST 1.1 criteria (e.g. median PFS, PFS rate at 12 and 18 months)

Overall survival (OS) for the three different populations, defined as the time from date of start of treatment to date of death due to any cause.
	
Overall survival (OS) (e.g. OS rate at 12 and 24 months)

Overall response rate (ORR) for the three different populations, defined as complete response or partial response as defined by RECIST 1.1
	
Overall Response Rate (ORR) after 24 weeks

To evaluate the safety and tolerability of ribociclib in combination with letrozole (and goserelin in premenopausal patients)
	
Frequency/severity of AEs AEs of special interest: Frequency, severity, frequency per patient, time to Event, duration of Event and recurrence

To evaluate patient reported outcomes for health related quality of life
	
Laboratory values Time to 10% deterioration in the global health status/QOL scale score of the EORTC QLQ-C30

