2.13 Other Exploratory analyses

Multivariate regression analysis to identify prognostic factors for Neutropenia respectively AST/ALT increase.

This analysis was not foreseen in the study protocol but included on request of the principal investigator for the presentation of interim and final results.

Two separate multivariate regression analyses were calculated for these interesting events (dependent variables):

1. Neutropenia, selected from AE data set via PTs “neutropenia” and/or “neutrophil count decreased”
2. Increase in ALT or AST: Selected from AE dataset via PTs “ALANINE AMINOTRANSFERASE INCREASED” and/or “ASPARTATE AMINOTRANSFERASE INCREASED”

The following effects (without interactions) were investigated by Type 3 estimates and Wald's confidence intervals for Odds ratios:

- Age at baseline (categorical): <60 years, 60-70 years, and >= 70 years
- BMI at baseline (categorical, rounded to integers): < 20, 20-25, 26-29, and >30 kg/m²
- Presence (no vs. yes) of bone metastases at study start
- Use of chemo therapy as prior antineoplastic medication (no vs. yes)
- Therapy line: 1st, 2nd, and >= 3rd

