5.2.7 Adverse events of special interest

- Neutropenia = AE term: MedDRA Preferred Term “Neutropenia” (10029354)
- Hepatobiliary toxicity = AE term: MedDRA Preferred Term “Alanine aminotransferase increased” (10001551) or “Aspartate aminotransferase increased” (10003481), Toxicity grade “Grade 3” or “Grade 4”
- QT prolongation = AE term: MedDRA Preferred Term “Electrocardiogram QT prolonged” (10014387)

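### The neutropenia adverse event of special interest is defined by one preferred term in SAP 2.8.1.1 and 5.2.7 but by two in SAP 2.13, without a reason, so its summaries can miss patients and episodes

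*SAP*

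**What the plan says.** SAP 2.8.1.1 lists three adverse events of special interest (AESIs). The first is "Neutropenia (MedDRA Code 10029354", one code. SAP 5.2.7 repeats this as a derivation rule, "Neutropenia = AE term: MedDRA Preferred Term", and names only the term 'Neutropenia'.

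SAP 2.13 sets up two regressions. The outcome of the first is "Neutropenia, selected from AE data set via PTs “neutropenia” and/or “neutrophil count decreased". The section says that this analysis was "included on request of the principal investigator for the presentation of interim and final results", but not why its term list differs from the AESI list.

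SAP 1.2 places the AESI summaries under the secondary safety objective: "AEs of special interest: Frequency, severity, frequency per patient, time to Event, duration of Event and recurrence". The table in SAP 2.8.1 marks six outputs for AESIs: incidence, system organ class by PT, patient listing, time to event, duration, and recurrence or number of events per patient.

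**The concern.** The same toxicity has two operational definitions in one SAP. A patient whose low neutrophil count was coded only to the laboratory term is a neutropenia case in the 2.13 regression and not a case in the AESI tables. The 2.13 results are meant for presentation, so two different neutropenia counts could be shown from the same data.

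Neutropenia is one of three important identified risks named in Protocol 1.2.6, and the AESI summary is where its onset, duration and recurrence are described. Laboratory data do not fill the gap. Protocol 7.2.2.4 keeps laboratory values out of the eCRF unless clinically significant, and SAP 2.8.3 only lists the relevant ones. The AESI summary therefore depends on adverse event coding.

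The other two AESIs already include laboratory or test-result terms: hepatobiliary toxicity pools the ALT and AST terms, and QT prolongation uses an ECG term. Only neutropenia leaves out its laboratory term.

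**Working it through.** The SAP gives no figure on this point, so the size has to come from the protocol's background tables, used as a proxy.

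**Inputs**
- Protocol Table 1-5 (earlier phase III trial, ribociclib plus letrozole, suspected-related events, N = 334): 'Neutropenia' 199; "Neutrophil count decreased" 63.
- Protocol Table 1-2 (phase Ib study, suspected-related events, N = 47): 33 and 8.
- Overlap within patients: not reported in either table, so it is bounded.

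**Formulas.** Let a be patients with 'Neutropenia', b patients with 'neutrophil count decreased', and o patients with both. Then:
- patients with either term = a + b − o
- patients missed by the one-term definition = b − o
- share missed of patients with either term = (b − o)/(a + b − o)
- share missed of all treated patients = (b − o)/N

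The overlap o lies between max(0, a + b − N) and min(a, b).

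**Step 1: reproduce the tables.** 199/334 = 59.6% and 63/334 = 18.9%; 33/47 = 70% and 8/47 = 17%. All agree with the printed values.

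**Step 2: bounds.** In both tables a + b is below N (262 against 334; 41 against 47), so o can be 0.

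| Source | Overlap | Either term | Missed | Of either term | Of all treated |
|---|---|---|---|---|---|
| Table 1-5 | full, o = 63 | 199 (59.6%) | 0 | 0% | 0% |
| Table 1-5 | none, o = 0 | 262 (78.4%) | 63 | 63/262 = 24.0% | 63/334 = 18.9% |
| Table 1-2 | full, o = 8 | 33 (70%) | 0 | 0% | 0% |
| Table 1-2 | none, o = 0 | 41 (87.2%) | 8 | 8/41 = 19.5% | 8/47 = 17.0% |

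**Step 3: causality basis.** AESIs are counted whatever the causality, while Table 1-5 holds suspected-related events only. Protocol 1.2.6 gives neutropenia in the same trial as 60.8% irrespective of causality. The all-causality rate of the second term must be at least 18.9%, because suspected-related cases are a subset. At that floor, no overlap gives 60.8 + 18.9 = 79.7% with either term, and 18.9/79.7 = 23.7% missed. Full overlap again gives 0. The range hardly moves.

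**Step 4: illustration only.** If the two terms were independent in Table 1-5, o = 199 × 63/334 = 37.5. The missed number would be 25.5 of 224.5 (11.3% of either term, and 25.5/334 = 7.6% of all treated). In Table 1-2, o = 33 × 8/47 = 5.6 and the missed number is 2.4 of 35.4 (6.7%). Nothing in the documents supports independence. If sites tend to use one term or the other, the true value lies nearer the upper bound.

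**Step 5: is the omitted term a mild variant?** Table 1-5 tabulates by maximum grade. Grade 3 or 4 accounts for (44 + 3)/63 = 75% of patients with the laboratory term and (130 + 29)/199 = 80% with 'Neutropenia'. It is not.

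**Step 6: the zero bound covers incidence only.** Even with full overlap, a patient whose first episode was coded to the laboratory term gets a later first onset. Episodes under that term also drop out of duration and recurrence.

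**The case against.** The strongest reply is that SAP 2.13 was never meant to mirror the AESI list. It is an exploratory regression added on request, and it is also broader for liver events: it selects the ALT and AST terms without the Grade 3 or 4 limit of 2.8.1.1. Both of its outcomes are wider than the AESI versions, which looks like separate event selection. This stands. A reader might infer from 2.13 that the AESI list contains an oversight; the documents do not show that.

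Second, the one-term definition has a possible rationale. Protocol 1.2.6 reports neutropenia (60.8%) separately from decreased neutrophil count in the earlier trial that this study is meant to support, so a single-PT row can be compared directly with it. This also stands as a possibility, but the SAP does not say so. It is a reason to keep the single-PT row, not to leave the difference unexplained.

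Third, the impact is limited. Every treatment-emergent event stays in the general PT and maximum-severity tables, so the tempting inference that events vanish from safety reporting is wrong. But two PT rows cannot be added into a patient count when overlap is unknown, and they give no onset, duration or recurrence. The AESI item also appears in SAP 1.2 and not in Protocol Table 3-1, so it is an SAP commitment only.

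Fourth, Protocol 8.1.2.1 tells sites: "Whenever possible, a diagnosis, rather than a symptom should be provided (e.g. anemia instead of low hemoglobin". That may reduce coding to the laboratory term alone but does not exclude it, since the instruction is conditional.

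**Conclusion.** The point holds as an unexplained inconsistency with a practical consequence. Following SAP 2.8.1.1 and 5.2.7 as written can understate the neutropenia AESI rate and misstate first onset, duration and recurrence. The primary endpoint and the general safety tables are unaffected.

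On proxy rates the one-term definition misses 0 to 24.0% of patients with either term (0 to 18.9% of all treated) from Table 1-5, and 0 to 19.5% of patients with either term from Table 1-2. If all 500 planned patients were treated, the Table 1-5 rates would mean 0 to 94 patients (63/334 × 500 = 94.3). These ranges assume that coding here resembles the earlier trials, and they are wide because overlap is not reported. The size in this trial is unknown. A reader might take a central value such as 11% as the expected loss; that rests on independence alone and should not be quoted as an estimate.

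**What to change.** In SAP 2.8.1.1 and 5.2.7, define the neutropenia AESI as PT 'Neutropenia' or PT 'Neutrophil count decreased'.

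- **Incidence:** count each patient once.
- **First onset:** take the earliest start of either PT.
- **Duration and number of events:** use the recorded entries of both PTs and collapse only entries with the same start date. Do not merge entries on imputed end dates. SAP 5.4.6 pushes missing end dates as late as possible, so such merging could chain separate episodes and change duration and recurrence for reasons unrelated to the added term.
- **Comparability:** keep the single-PT row beside the new one, for comparison with the earlier trial's 60.8% and with any interim AESI tables. Whether such tables exist cannot be seen here, because SAP 2.1 refers to RAP 7.2 for them.
- **Record:** note the revised definition in 2.8.1.1 and 5.2.7 themselves. SAP section 4 covers changes to protocol-specified analyses, and the protocol's analysis section defines no AESI.

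If the one-term definition is deliberate, a sentence saying why it differs from 2.13 is the minimum. It would explain the difference but would not recover the onset, duration and recurrence of the omitted episodes.

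The cost is reprogramming the six AESI outputs for cohorts A, B1, B2, B and total. The reported AESI rate may rise, or stay the same if the terms overlap fully. No new data are needed.

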6.2.1.2 Additional follow-up for hepatic toxicities

Increase in transaminases combined with total bilirubin (TBIL) increase may be indicative of drug-induced liver injury (DILI), and should be considered as clinically important events. A study with ribociclib in non-cancer patients with varying degrees of hepatic impairment (mild, moderate, severe based on Child-Pugh classification) matched subjects with normal hepatic function was completed (CLEE011A2109). Refer to [Ribociclib Investigators Brochure] for more details.

The threshold for potential DILI may depend on the patient's baseline AST/ALT and TBIL value; patients meeting any of the following criteria will require further follow-up as outlined below:

- For patients with normal ALT and AST and TBIL value at baseline: AST or ALT $> 3.0 \times$ ULN combined with TBIL $> 2.0 \times$ ULN
- For patients with elevated AST or ALT or TBIL value at baseline: [AST or ALT $> 2 \times$ baseline AND $> 3.0 \times$ ULN] OR [AST or ALT $> 8.0 \times$ ULN], whichever is lower, combined with [TBIL $> 2 \times$ baseline AND $> 2.0 \times$ ULN]

Medical review needs to ensure that liver test elevations are not caused by cholestasis, defined as: ALP elevation $> 2.0 \times$ ULN with R value < 2 in patients without bone metastasis, or elevation of ALP liver fraction in patients with bone metastasis.

Note: The R value is calculated by dividing the ALT by the ALP, using multiples of the ULN for both values. It denotes the relative pattern of ALT and/or ALP elevation is due to cholestatic or hepatocellular liver injury or mixed type injury).

In the absence of cholestasis, these patients should be immediately discontinued from study drug treatment, and repeat LFT testing as soon as possible, preferably within 48 hours from the awareness of the abnormal results. The evaluation should include

laboratory tests, detailed history, physical assessment and the possibility of liver metastasis or new liver lesions, obstructions/compressions, etc.

Hepatic toxicity monitoring includes the following LFTs: albumin, ALT, AST, total bilirubin, direct and indirect bilirubin, alkaline phosphatase (fractionated if alkaline phosphatase is grade 2 or higher), creatine kinase (CK), prothrombin time (PT)/INR and GGT. For patients with Gilbert Syndrome: total and direct bilirubin must be monitored, intensified monitoring applies to changes in direct bilirubin only.

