Close observation is recommended in case of AST, ALT, and/or bilirubin increase requiring dose interruption, which involves:

- Repeating liver enzyme and serum bilirubin tests **two or three times weekly**. Frequency of re-testing can decrease to once a week or less if abnormalities stabilize or return to normal values.
- Obtaining a more detailed history of current symptoms.
- Obtaining a more detailed history of prior and/or concurrent diseases, including history of any pre-existing liver conditions or risk factors.
- Obtaining a history of concomitant drug use (including non-prescription medications, herbal and dietary supplements), alcohol use, recreational drug use, and special diets.
- Ruling out acute viral hepatitis types A, B, C, D, and E; hepatotropic virus infections (CMV, EBV or HSV); autoimmune or alcoholic hepatitis; NASH; hypoxic/ischemic hepatopathy; and biliary tract disease.
- Obtaining a history of exposure to environmental chemical agents.
- Obtaining additional tests to evaluate liver function, as appropriate (e.g., INR, direct bilirubin).
- Considering gastroenterology or hepatology consultations.
- Assessing cardiovascular dysfunction or impaired liver oxygenation, including hypotension or right heart failure as possible etiologies for liver dysfunction.
- Liver biopsy as clinically indicated to assess pathological change and degree of potential liver injury.

All cases confirmed on repeat testing meeting the laboratory criteria defined above, with no other alternative cause for LFT abnormalities identified, should be considered as “medically significant”, thus met the definition of SAE (Section 8.2.1), and reported as SAE using the term “potential drug-induced liver injury”. All events should be followed up with the outcome clearly documented.

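### The SAP's hepatobiliary AESI rule can leave out cases that the protocol requires to be reported as potential drug-induced liver injury

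*SAP*

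**What the plan says.** SAP 2.8.1.1 names three adverse events of special interest. The liver item is "Hepatobiliary toxicity, defined as grade 3 or 4 increases in ALT or/and AST (MedDRA Codes: 10001551, 10003481"). SAP 5.2.7 gives the programming rule, which begins "Hepatobiliary toxicity = AE term: MedDRA Preferred Term" and admits only the preferred terms ALT increased and AST increased, at grade 3 or 4. There is no drug-induced liver injury term in either place.

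Protocol 6.2.1.2 starts from a different idea of a liver event: "Increase in transaminases combined with total bilirubin (TBIL) increase may be indicative of drug-induced liver injury (DILI"). For a patient with normal baseline values the criterion is "AST or ALT $> 3.0 \times$ ULN combined with TBIL $> 2.0 \times$ ULN", and a corresponding criterion applies when baseline is elevated. If repeat testing confirms the finding and no other cause is identified, the case is medically significant, "thus met the definition of SAE (Section 8.2.1), and reported as SAE using the term" *potential drug-induced liver injury*.

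Two recording rules bear on what else a site enters. Protocol 8.1.2.1 asks for the diagnosis where there is one: "Whenever possible, a diagnosis, rather than a symptom should be provided (e.g. anemia instead of low hemoglobin"). It also says that a laboratory result belonging to an adverse event already reported need not be entered as a further event. Protocol 8.1.1 states the same preference for a diagnosis over its component signs.

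**The concern.** The protocol's reporting rule and the SAP's selection rule do not meet. A site that follows Protocol 6.2.1.2 files the case under a term that the AESI rule does not name, and it has no duty to add a parallel enzyme entry. Even where it does add one, the grade filter can reject it.

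This matters because Protocol 1.2.6 lists hepatobiliary toxicity among three important identified risks of ribociclib, and SAP 1.2 makes frequency, time to event, duration and recurrence of AESIs named safety endpoints. Someone reading an AESI line called hepatobiliary toxicity would expect it to include the combined transaminase and bilirubin cases that the protocol singles out as serious. As the rule stands, it may hold isolated enzyme rises and omit some of those cases. Laboratory values will not repair this, since SAP 2.8.3 only lists them.

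**Working it through.** The plan states no figure to reproduce here. The check compares the two definitions and then sets a scale.

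**1. Term.** Protocol 6.2.1.2 requires the term *potential drug-induced liver injury*. SAP 5.2.7 selects ALT increased (10001551) and AST increased (10003481). The mandated term names neither enzyme, so it probably codes elsewhere, but the documents do not show the coding. On that assumption, a case recorded only under the mandated term is not selected at any grade.

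**2. Grade, normal baseline.** Protocol Table 6-4 grades transaminases above 3.0 and up to 5.0 x ULN as 2, above 5.0 and up to 20.0 as 3, and above 20.0 as 4. Assume that bilirubin is above 2 x ULN throughout:

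| ALT or AST (x ULN) | Meets the DILI transaminase limit (> 3.0) | Grade | Passes the AESI grade filter |
|---|---|---|---|
| 3.1 | yes | 2 | no |
| 4.0 | yes | 2 | no |
| 5.0 | yes | 2 | no |
| 5.1 | yes | 3 | yes, if recorded as ALT or AST increased |
| 8.0 | yes | 3 | yes, if recorded as ALT or AST increased |
| 21.0 | yes | 4 | yes, if recorded as ALT or AST increased |

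In the 3 to 5 x ULN band a case fails the filter even with a parallel enzyme entry.

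**3. Grade, elevated baseline.** The transaminase limit is the lower of (a) 8.0 x ULN and (b) the larger of 2 x baseline and 3.0 x ULN. At a baseline of 2.0 x ULN, the limit is min(8.0, max(2 x 2.0, 3.0)) = 4.0 x ULN, which is still in the grade 2 band. The gap is therefore not confined to patients with normal baseline.

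**4. Where such a case still appears.** The table in SAP 2.8.1 marks treatment-emergent serious AEs for incidence, system organ class by preferred term, listing, maximum severity, time to event, duration and recurrence. Confirmed potential DILI is an SAE by rule, so every treatment-emergent case enters that row. The row covers serious events as a class, and the SAP specifies no liver-specific version of it.

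**5. Scale.** Protocol 1.2.6 reports for the pivotal trial: "Four patients met the criteria for Hy's Law in ribociclib plus letrozole group". Protocol Table 1-5 gives 334 patients in that arm.

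- Rate: 4/334 = 1.2%.
- Exact (Clopper-Pearson) 95% limits: lower = Beta quantile at 0.025 with parameters 4 and 331 = 0.33%; upper = Beta quantile at 0.975 with parameters 5 and 330 = 3.04%.
- In 500 patients: 500 x 4/334 = 6.0, with range 500 x 0.00327 = 1.6 to 500 x 0.03038 = 15.2.

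These are potential cases, not missed cases.

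**The case against.** The best reply is that nothing is lost. As step 4 shows, the serious AE row carries every type of summary that the AESI row does, and maximum severity as well. Table 6-4 calls for discontinuation of ribociclib when the combined criterion is met without cholestasis, so these cases should also appear in the table of events leading to discontinuation, and the listings give verbatim term, onset and action taken. This stands. A reader might infer that the most serious liver cases vanish from the safety report, or lack onset, duration and recurrence results. The documents do not support that. Only the liver-specific grouping is missing.

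A second reply is that an enzyme entry will often exist anyway. Protocol 8.1.2.1 makes a laboratory abnormality that changes study treatment an adverse event, and Table 6-4 changes treatment for new grade 2 and higher transaminase rises. The DILI term applies only after repeat testing, by which time ALT or AST increased may already be on the form. This stands in part: overlap could be large. It is not assured, because the recording rules allow the enzyme result to be subsumed under the diagnosis, and it does not help in the grade 2 band.

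Third, grade 3/4 ALT and AST is how Protocol 1.2.6 itself first quantifies the risk, so the definition is a reasonable one for comparison. That is a good reason to keep the line, but not to let it stand alone, since the same paragraph goes on to report Hy's Law cases.

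**Conclusion.** The point holds as a gap in grouping. The hepatobiliary AESI rule can undercount the protocol's own potential DILI cases, either through the term or through the grade filter. The term route rests on the assumption that the mandated term does not code to ALT or AST increased. The grade route needs no coding assumption.

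The size is unknown. About 6 of 500 patients (2 to 15) would be potential cases if the pivotal trial's rate carries over and its Hy's Law criteria resemble those of Protocol 6.2.1.2. A reader might take 6 as the number missed. The protocol gives neither the transaminase grade nor the coded term of the four pivotal cases, so anything from none to all might be missed.

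Nor do the documents show that bilirubin terms or a broader set of hepatic diagnoses must be added. The inconsistency concerns only the event that the protocol defines and names.

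**What to change.** In SAP 2.8.1.1 and 5.2.7, present hepatobiliary toxicity of special interest on three lines:

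1. ALT or AST increased at grade 3 or 4, unchanged, so that it stays comparable with earlier ribociclib results.
2. Events reported as potential drug-induced liver injury, at any transaminase grade, selected by whichever preferred term the verbatim term was coded to. State that preferred term.
3. Patients with either.

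Give each line the same incidence, time-to-event, duration and recurrence summaries. No new data are needed. The cost is a short wording change, a check of the coding and modest programming. If the tables already exist, a supplementary table is enough.

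The downside is that the combined rate may be slightly higher than the enzyme line alone. At the pivotal rate the increase would be at most 1.2 percentage points (3.0 at the upper confidence limit), and only if every potential case were otherwise missed.
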